2.2 Study Rationale

[figure not shown]
Behavioral health interventions have promise to decrease depression and ameliorate insulin resistance.

We conducted an initial single-site, randomized controlled efficacy trial (NIH/NICHD Grant# K99HD069516) to determine if intervening to decrease depression with the standard-of-care—cognitive-behavioral therapy (CBT)—would ameliorate insulin resistance in adolescents at-risk for T2D. Teens were randomized to a 6-week group CBT vs. 6-week health education (HealthEd) control group. In adolescents with elevated depression, CBT (vs. HealthEd) led to greater decreases in depression at post-treatment,⁵⁶ and lower 2-hour insulin after an oral glucose challenge at 1-year follow-up.⁵⁷ Also among those with elevated depression symptoms, CBT (vs. HealthEd) indirectly led to greater post-treatment to 1-year decreases in insulin resistance through decreasing depression during treatment.⁵⁸ All of the effects from this trial were independent of initial BMI, body fat, and body fat change.⁵⁶⁻⁵⁸ These findings laid a foundation for the notion that brief, behavioral health interventions to decrease elevated depression symptoms may lessen T2D risk in adolescents, even in the absence of weight loss.

Mindfulness-based intervention (MBI) for psychological-physical integrative health. There has been rising scientific and clinical interest in MBI to decrease psychological distress^{59,60} (e.g., depression) and improve physical health (e.g., cardiometabolic health).⁶¹⁻⁶³ A principal MBI goal is increasing dispositional mindfulness, the propensity to pay attention on purpose to one's present-moment experiences with an attitude of non-judgment and equanimity.⁶⁴ From the framework of Monitor and Acceptance Theory,^{65,66} MBI is postulated to decrease depression and improve stress-related behavior and physiology through (i) increased attention to monitoring of present-moment experiences, combined with (ii) increased acceptance of experiences

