regardless of their valence, mechanisms supported in recent MBI dismantling studies.^{65,67-69} As show in **Figure 1** below, MBI is theorized to be particularly fitting for decreasing depression and improving insulin resistance in teen at-risk for T2D. MBI is postulated to: (a) alleviate ruminative, negative thoughts that perpetuate and exacerbate depression,⁷⁰⁻⁷² (b) ameliorate dysregulated stress physiology including cortisol dysregulation and stress reactivity, shown to promote insulin resistance and adverse metabolic outcomes,^{73,74} and (c) lessen stress-related behavior such as hedonic eating, or eating for reward/pleasure as opposed to physiological hunger,⁷⁵ and physical inactivity.⁷⁶ Adolescent depression symptoms relate to increases in cortisol dysregulation,^{77,78} stress reactivity,⁷⁹ hedonic eating,⁸⁰⁻⁸² and physical inactivity,⁸³ which, in turn, have each been related to increased insulin resistance independent of obesity.⁸⁴⁻⁹⁷ Enhanced monitoring and acceptance of thoughts, emotions, and body sensations as they unfold moment-to-moment is theorized to improve stress-related behavior/physiology through its impact on decreasing depression; yet, one distinctive benefit of MBI may be its potential to offer direct, salutary effects for stress behavior/physiology. MBI may improve identification of cues (e.g., negative affectivity) that prompt behaviors triggered by stress, and to tolerate distress without acting habitually.⁹⁸ MBI also may improve executive function, including the ability to flexibly deploy attention away from cues that prompt stress-behavior and heighten stress physiology.^{59,99}

Figure 1. Theoretical MBI, vs. CBT, effects on depression & insulin resistance by decreasing (a) depression, (b) stress physiology, and (c) stress-related behavior

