Another purpose of secondary analyses is to supplement the mixed-methods analyses in Aim 3 used to refine study procedures and interventions in preparation for a future efficacy trial by understanding predictors associated with study outcomes, as well as mediators and moderators of intervention effects. This study is not designed as an efficacy study, and we will not necessarily have sufficient statistical power for the secondary analyses. However, results of these analyses may help inform changes to the interventions. We will examine predictors of participant attrition, attendance, and likability/credibility ratings. We will use multilevel mixed-effects models to examine change over time in measures of depression, insulin resistance, stress-related behavior, and stress physiology. These models will allow us to account for and estimate the correlation within study site and intervention cohort, as well as the correlation between repeated measures within a participant. ICC will be estimated using the method of Donner¹⁷⁹ for continuous variables and Ridout¹⁸⁰ for binary variables. The models will contain terms for group, time, and a group by time interaction. We will adjust for the baseline value of the outcome, and will also consider adjustment for baseline age, sex, race/ethnicity, particularly if these variables are not balanced across study groups. Models will be adjusted for baseline adiposity and change in adiposity to examine whether decreases in depressive symptoms improves insulin sensitivity independent of adiposity. If we find significant between-group differences in the insulin resistance, stress-related behavior, and stress physiology outcomes, we will test whether those effects are moderated by baseline depressive symptom severity (CES-D score) by including an interaction term in the model. We will also examine participant characteristics associated with these outcomes in order to better understand factors that moderate the response to intervention. Mediation analyses, using the product-of-coefficients method and bootstrapped standard errors, will be used to explore whether improvements in insulin sensitivity (if present) are mediated by changes in stress-related behaviors and stress physiology. Quantitative measures of group cohesion, therapeutic alliance, and perceived credibility/expectancy, summarized by intervention arm, will inform modifications to facilitator training, optimization of interventions, and study design in the larger trial. Finally, we will examine theoretical therapeutic mechanisms to explore the hypotheses that in MBI, mindfulness, monitoring/acceptance, and executive function will improve and in CBT, thoughts and pleasant activities will improve, compared to each other and to HealthEd.

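### The insulin-sensitivity models in section 8.6.2 are said to test whether falling depression helps, but they contain no term for change in depression, and depression is not a listed mediator

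*Combined protocol and SAP*

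**What the plan says.** All of the relevant specification is in section 8.6.2 (Secondary Analyses).

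- Outcomes: "We will use multilevel mixed-effects models to examine change over time in measures of depression, insulin resistance, stress-related behavior, and stress physiology". Depression is an outcome in its own right here, alongside insulin resistance.
- Fixed effects: "The models will contain terms for group, time, and a group by time interaction".
- Covariates: "We will adjust for the baseline value of the outcome, and will also consider adjustment for baseline age, sex, race/ethnicity".
- Adiposity: "Models will be adjusted for baseline adiposity and change in adiposity", and the purpose given for this is "to examine whether decreases in depressive symptoms improves insulin sensitivity independent of adiposity".
- Mediation: a product-of-coefficients analysis will explore whether improvements in insulin sensitivity "are mediated by changes in stress-related behaviors and stress physiology".
- Moderation: baseline CES-D enters through an interaction term, and only if arms differ significantly on the outcome.

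Section 2.2 supplies the background. In the team's earlier trial, CBT "indirectly led to greater post-treatment to 1-year decreases in insulin resistance through decreasing depression during treatment". Section 2.2 also proposes that "one distinctive benefit of MBI may be its potential to offer direct, salutary effects for stress behavior/physiology", and it links that behavior and physiology to insulin resistance.

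**The concern.** The stated purpose concerns an effect of falling depression on insulin sensitivity. A model answers that only if some coefficient connects change in depression to the insulin outcome. The listed models have none, and no other planned analysis supplies one.

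The depression-to-insulin link is the rationale for the program (sections 2.1 and 2.2), and section 8.6.2 says the secondary analyses should help explain mediators and moderators before the efficacy trial. A reader who takes the stated purpose at face value would read the arm result as evidence on the link. That can mislead in two ways. An arm difference could come from the direct MBI route that section 2.2 allows and be credited to depression. Or a real link could go unseen because the arms differ only modestly on depression.

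**Working it through.** **Step 1. Compare the question with the terms.** The plan gives no figure for this point, so the first check is structural. Depression appears in the secondary analyses in these roles:

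- As a separate outcome. Two parallel outcome models do not estimate the association between the two changes.
- As a baseline moderator, conditional on a significant arm difference. This asks whether the arm effect varies with starting severity.
- Not among the insulin mediators.
- Not by name among the participant characteristics examined, which are framed as moderators. The predictor analyses for attrition, attendance and likability/credibility ratings do not concern insulin.

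In the insulin model, group and group-by-time estimate arm differences given adiposity. Their null hypothesis is that arms do not differ. This is a different hypothesis from the one stated, and a larger sample would not change that.

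**Step 2. Inputs for an illustration.**

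- Completers per arm: 40 x 0.70 = 28 (1-year retention threshold, section 9.3.2) and 40 x 0.85 = 34 (15% loss, section 8.2).
- MBI minus CBT on depression: 0.56 SD (post-treatment, section 2.2).
- Assumed: CBT minus HealthEd on depression 0.3 SD; path from depression change to insulin sensitivity 0.3 to 0.4 SD per SD.

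**Step 3. What the arm contrast sees if the link is real.** Implied arm difference = path x arm difference in depression.

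- MBI vs CBT: 0.3 x 0.56 = 0.17 SD to 0.4 x 0.56 = 0.22 SD.
- MBI vs HealthEd: 0.3 x 0.86 = 0.26 SD to 0.4 x 0.86 = 0.34 SD, where 0.86 = 0.56 + 0.3.

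The standard error of an arm difference is about sqrt(2/n) residual SDs: 0.27 at n = 28 and 0.24 at n = 34. The expected contrasts are therefore about 0.6 (0.168/0.267) to 1.4 (0.344/0.243) standard errors.

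**Step 4. Simulated rejection rates.** These use linear models at one follow-up, adjusted for baseline outcome and change in adiposity, with 28 to 34 per arm. The arm test is a two-sided 5% F test on 2 df unless stated.

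- No depression effect, direct MBI effect: the arm test rejects in 57-67% of runs at 0.5 SD and 89-95% at 0.73 SD (the size of the 1-year d for insulin resistance in section 2.2).
- No depression effect, with both active arms better by 0.6 SD on depression and by 0.8 SD directly on insulin: 85.9% (n = 28) and 92.1% (n = 34).
- Real link as in step 3: the arm test rejects in 13-24% of runs; the coefficient of an added CES-D-change term is significant in 85-99%.

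**Step 5. Two checks on those rates.**

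- *Criterion.* For signals of effect, section 8.6.2 specifies one-sided 80% intervals. Their margin is about 0.84 x sqrt(2/n) = 0.22 SD at n = 28 and 0.20 SD at n = 34, so the MBI-HealthEd difference of 0.26 to 0.34 SD often clears it. In the real-link scenario the bound excludes zero in 58-72% of runs.
- *Confounding.* With no depression effect, the CES-D-change term rejects in about 5% of runs only if nothing drives both changes. With a shared residual correlation of 0.2 or 0.3 (assumed), it rejects in about 44-50% or 78-85%.

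**The case against.** The case on the other side has four parts.

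1. *Stakes.* Depression and insulin sensitivity are not among the primary or secondary endpoints in sections 3.2, 3.3 and 8.5, all of which concern fidelity, feasibility and acceptability. Section 8.6.2 says the study is not designed for efficacy and may lack power here. This stands, and it limits the point. It does not remove the mismatch, which is about what is estimated rather than how precisely.

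2. *Loose wording.* The clause may be shorthand for an adiposity-adjusted arm comparison. Section 2.2 describes the earlier trial as intervening on depression and reports effects independent of body fat. The model fits that reading, so rewording is an acceptable minimum remedy. As it stands, however, the clause makes falling symptoms the cause under study.

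3. *The illustration flatters the alternative.* Change in depression is not randomized. A nominal error rate for the CES-D-change term depends on there being no shared cause, and step 5 shows how fast it is lost. This stands: the added term answers the right question, but only as an association.

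4. *The low arm-test power is not the plan's own criterion.* This also stands. The two-sided 5% F test at one visit is neither the one-sided 80% interval nor the planned repeated-measures model with site and cohort clustering. The looser criterion does not rescue the inference, because an arm difference that clears it still does not show that depression was the route.

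A reader might also infer from section 7.2 that all arms will improve equally on depression, leaving the arm comparison blind to the link. The text does not support that. It expects HealthEd to improve less than MBI and CBT, with possibly more improvement in MBI.

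**Conclusion.** The mismatch is real and rests on the text of section 8.6.2 alone: no planned coefficient links change in CES-D to insulin sensitivity, so following the plan answers a different question from the one stated. An arm difference would not establish the depression link, and its absence would not refute the link.

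The size is illustrative only. The rejection rates depend on assumed paths and arm differences, on a simplified single-visit model and, for the CES-D-change term, on no confounding. The 85-99% applies to that coefficient. The indirect effect also needs arms to differ on depression, so its power will be lower.

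Two stronger readings are tempting and unsupported. One is that adding the CES-D term gives a well-calibrated test of cause, which the confounding check rules out. The other is that the trial's main conclusions are at risk; the feasibility and fidelity endpoints do not use these models. The consequence is confined to a secondary, exploratory conclusion about mechanism, though one that the efficacy trial is meant to draw on.

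**What to change.** In section 8.6.2:

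1. Add change in CES-D from baseline to 6-week follow-up as a named mediator in the existing product-of-coefficients analysis, with 1-year ISI and HOMA-IR as outcomes, so that the mediator precedes the outcome.
2. Adjust for arm, the baseline insulin measure, baseline CES-D, baseline adiposity and change in adiposity. The last term matches the stated independence from adiposity; show results with and without it.
3. State that the group-by-time model tests only whether arms differ.
4. State that the CES-D-to-insulin path will be reported as associational, because change in depression is not randomized and shared causes could produce it.

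At minimum, reword the clause so that it describes an adiposity-adjusted comparison of arms and makes no claim about falling depressive symptoms.

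The full change costs one added analysis and a few sentences. Section 6.2.6 already schedules CES-D and the oral glucose tolerance test at both follow-ups, so no new data are needed. The rewording alone costs one sentence but leaves the depression question unanswered.

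### The interaction with baseline CES-D is fitted only after a significant arm difference, so the one moderator the plan names may often go unestimated

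*Combined protocol and SAP*

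**What the plan says.** Section 8.6.2 gives as one purpose of the secondary analyses "understanding predictors associated with study outcomes, as well as mediators and moderators of intervention effects". It warns that "we will not necessarily have sufficient statistical power for the secondary analyses".

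For the outcomes beyond depression it then sets a condition: "If we find significant between-group differences in the insulin resistance, stress-related behavior, and stress physiology outcomes, we will test whether those effects are moderated". The moderator named is the baseline CES-D score, tested through an interaction term. The plan does not say what level counts as significant, which arm contrast is meant, or whether the condition applies outcome by outcome or needs all three outcome groups.

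The next sentence has no such condition: "We will also examine participant characteristics associated with these outcomes in order to better understand factors that moderate the response to intervention". It names neither CES-D nor an interaction term.

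Two other places bear on the point. Section 4.1 admits only adolescents with a CES-D total above 20. Section 2.2 describes the sponsor's previous CBT trial: "In adolescents with elevated depression, CBT (vs. HealthEd) led to greater decreases in depression at post-treatment".

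**The concern.** A test of the average arm effect and a test of whether the effect varies with baseline severity answer different questions. An intervention that helps mainly the more depressed participants can have a modest average effect, and the first test may then miss it. Under the plan as written, the interaction would not be fitted in that case. The plan also relies, as its precondition, on a test from a group of analyses it describes as possibly underpowered.

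This sits awkwardly with the rest of 8.6.2. That section says that if no effect appears, the possible reasons should be considered before the main trial is designed. Response that varies with severity is one such reason, and the condition switches off the named check for it in just that situation.

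What is at stake is design information for the efficacy trial: whether response to the interventions depends on how severe symptoms are at entry. The data needed to estimate this are already being collected.

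**Working it through.** **The plan's own figure.** No figure is given for the moderation test or its precondition. The only effect size in 8.6.2 is 0.3 SD, tied to a one-sided 80% confidence interval. The final sample size and power are not stated, so 0.3 cannot be uniquely reproduced. It is consistent as a confidence bound: 0.842 × √(2/32) = 0.21 at 32 per arm, which is below 0.3.

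**Inputs from the documents**
- 32 per arm: 4 clusters × 8 participants (section 8.2, Aim 2).
- Average effect 0.3 SD (section 8.6.2), and 0.73 SD for insulin resistance at 1 year in the previous single-site MBI pilot (section 2.2).

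**Assumptions, not in the documents**
- One pair of arms, independent observations, standard-normal baseline CES-D.
- Baseline-outcome correlation 0.4, so residual SD = √(1 − 0.4²) = 0.917.
- Precondition and interaction both tested at two-sided 5%, unless stated.
- Interaction slope 0.5 or 0.3 SD of outcome per SD of CES-D. A further case confines the effect to the upper half: 0 below the CES-D mean and 0.6 above it, so the average is 0.3.

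**Step 1: interaction always fitted.** SE of the slope ≈ 0.917 × √(2/32) = 0.229.
- Slope 0.5: 0.5/0.229 = 2.18, and Φ(2.18 − 1.96) = 0.59. Simulation gives 54%, because it uses t critical values and a random moderator.
- Slope 0.3: 0.3/0.229 = 1.31, and Φ(1.31 − 1.96) = 0.26. Simulated: 25%.
- Upper half only: the equivalent linear slope is 0.6 × 0.399 = 0.24. Then 0.24/0.229 = 1.05, and Φ(1.05 − 1.96) = 0.18. Simulated: 17%.

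**Step 2: chance that the precondition is met.** The arm model omits the interaction, which adds (0.5/2)² = 0.0625 to the residual variance at slope 0.5. The SE is then √(0.84 + 0.0625) × 0.25 = 0.237.
- Average 0.3, two-sided 5%: Φ(0.3/0.237 − 1.96) = Φ(−0.69) = 0.24.
- Average 0.3, one-sided 0.20: Φ(1.27 − 0.84) = 0.66.
- Average 0.73, two-sided 5%: Φ(3.08 − 1.96) = 0.87.

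A plain two-sample t-test at d = 0.3, without the baseline covariate, gives 22% at 32 per arm and 20% at 28.

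**Step 3: both together.** With a centred moderator the two tests are nearly independent, so the chance of fitting and detecting the interaction is close to the product. For example, 0.24 × 0.54 = 0.13, against a simulated 11-12%.

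| Scenario, 32 per arm | Always fitted | Under the condition |
|---|---|---|
| Average 0.3, slope 0.5 | 54% | 11-12% |
| Average 0.3, slope 0.3 | 25% | 6% |
| Average 0.3, upper half only | 17% | 4% |
| Average 0.3, slope 0.5, one-sided 0.20 condition | 55% | 35% |
| Average 0.73, slope 0.5 | 54% | 45% |

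**Sensitivity.** A three-arm version used overall F-tests, no baseline-outcome correlation and 28 to 40 per arm. At average 0.3 it gave 44-58% against 8-14% for slope 0.5, and 17-25% against 4-6% for slope 0.3. At average 0.73 and slope 0.5 it gave 43-59% against 32-53%.

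**The case against.** Testing moderation only of effects that have been found is a recognised form of restraint. There are three outcome groups, three arms and two follow-ups, and the plan says openly that this is not an efficacy study. That has some force, but an exploratory label and a confidence interval limit over-reading equally well without discarding the estimate.

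The plan also has moderator work with no precondition, in the very next sentence. Baseline depression is a participant characteristic and could be examined there, so it would be wrong to infer that the plan closes off moderation altogether. But that sentence does not name CES-D, and a reader would reasonably take the explicit rule for CES-D to govern it.

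The size of the loss is open to challenge too, and this part stands. The largest contrast rests on an assumed slope of 0.5 and an assumed 5% level. An even starker case, zero average effect with slope 0.5 (55% against 2-3%), implies harm below average severity that mirrors the benefit above it, and nothing in the documents suggests that. With smaller slopes, power is poor even when the interaction is always fitted. Restricting entry to CES-D above 20 may narrow the moderator's range and lower it further.

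Finally, a reader might infer from section 2.2 that the condition hides the subgroup pattern seen in the previous CBT trial. The documents do not support this. Section 2.2 reports effects among adolescents with elevated depression, but gives no interaction test and no null overall result. Because everyone here must score above 20, a contrast of elevated with non-elevated symptoms is unavailable whether or not the condition is kept. Only a gradient in severity above 20 could be missed.

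**Conclusion.** The point holds as a minor one. The plan ties its one named moderator analysis to a significance test that moderation does not require, leaves that test undefined, and so works against its own aim of learning about moderators. At the plan's own effect size of 0.3, with an assumed two-sided 5% condition, the interaction would go unfitted in roughly three trials out of four (1 − 0.24 = 0.76), and the chance of detecting it falls to about a quarter or less of its unconditional value.

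That proportion is not a general fact about this trial. At the previous pilot's 0.73, which section 2.2 calls preliminary, or with a one-sided 0.20 condition, the interaction would usually be fitted. It would therefore be too strong to say that most trials with real moderation would never examine it. The slopes, the significance level, the baseline correlation and the normal moderator are all assumptions. No primary outcome and no secondary endpoint listed in section 8.5.2 is affected.

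**What to change.** In section 8.6.2, replace the conditional sentence with one stating that the arm-by-baseline-CES-D interaction will be estimated for each insulin resistance, stress-related behavior and stress physiology outcome whatever the p-value for the arm effect, reported with its confidence interval, and labelled exploratory. It would help to add that the estimate describes variation in severity within the enrolled range only.

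If the sponsor prefers to keep the condition, the plan should at least state its significance level, the arm contrast it refers to, and whether it applies to each outcome separately.

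The cost is one sentence and a few extra model fits on data already collected. The downside is a few more exploratory estimates to report, most of them imprecise.
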